1. INTRODUCTION

This statistical analysis plan (SAP) has been developed to supplement the statistical analyses described in the clinical study protocol (CSP) final version 2.0 dated 07 March 2022.

This current document describes the methodology and considerations of the planned analyses. The current document will be supplemented with a list of all the TFLs for this study and the corresponding shells.

Any changes to the analyses described in this document or additional analyses performed to supplement the planned analyses, will be described in the clinical study report (CSR).

The preparation of this SAP is based on the following documents:

- Good Clinical Practice (GCP) guidelines E6 (R1)
- International Council on Harmonization (ICH) E9 guideline entitled, "Guidance for Industry: Statistical Principles for Clinical Trials".
- ICH E3 guideline entitled, "Guidance for Industry: Structure and Content of Clinical Study Reports".
- ICH E9 (R1) addendum on "Estimands and sensitivity analysis in clinical trials".
- Clinical Study Protocol final version 2.0 dated 07 March 2022.

1.1 Revision History

Version	Date of Revision	Revision
Final version 1.0	21 Mar 2022	Original Version

Statistical Analysis Plan Number CA36095

2. OBJECTIVES AND ENDPOINTS

The estimands requested as per ICH guidelines for all objectives are listed in the protocol under Section 12.

Exploratory Objectives and Endpoints:

The objectives and endpoints of this study are:

1. To describe the plasma concentration-time profile of nicotine and derived pharmacokinetic (PK) parameters of 4 variants of Nicotine pouch (NP) 1.0 nicotine pouches compared to Velo-NP and Zyn-NP in healthy smokers from a 30 minutes product use period.

Endpoints

- Background-corrected maximum plasma concentration [C_{max}]
- Background-corrected time to the maximum concentration [T_{max}]
- Area under the background-corrected concentration-time curve (AUC) from start of product use (T₀), to all subsequent time points and extrapolated to infinity [AUC_{0-5min}, AUC_{0-10min}, AUC_{0-15min}, AUC_{0-20min}, AUC_{0-25min}, AUC_{0-30min}, AUC_{0-35min}, AUC_{0-40min}, AUC_{0-1h}, AUC_{0-3h}, AUC_{0-6h}, AUC_{0-infinity}]
- 2. To describe pharmacodynamic (PD) effects (subjective effects and related behavioral assessments) of 4 variants of NP 1.0 compared to Velo-NP and Zyn-NP in healthy smokers from a 30 minutes product use period.

Endpoints (Day 1 to Day 3)

- Score of cigarette craving by the visual analog scale (VAS)-craving assessment [VAS-C-15min, VAS-C5min, VAS-C10min, VAS-C15min, VAS-C20min, VAS-C25min, VAS-C30min, VAS-C35min, VAS-C40min, VAS-C1h, VAS-C3h, VAS-C6h]
- Score of "in the moment" product liking by the VAS-liking (in the moment) assessment [VAS-L5min, VAS-L10min, VAS-L15min, VAS-L20min, VAS-L25min, VAS-L30min, VAS-L35min, VAS-L40min, VAS-L1h, VAS-L3h]
- Score of overall product liking by the VAS-liking (overall) assessment
- Score of product satisfaction by the VAS- satisfaction assessment [VAS-S5min, VAS-S10min, VAS-S15min, VAS-S20min, VAS-S25min, VAS-S30min, VAS-S35min, VAS-S40min, VAS-S1h, VAS-S3h, VAS-S6h]
- Score of product intention to use again by the VAS-intention to use again assessment [VAS-ITU30min, VAS-ITU3h]
- Subscale scores from the Product Evaluation Scale (PES)
- Scores from items of the Sensory questionnaire
- 3. To evaluate the safety and tolerability during the study

Endpoints (from Enrollment to EOS):

- Incidence of adverse events (AEs) and serious adverse events (SAEs)
- Incidence of product events
- Changes in electrocardiogram (ECG) from baseline (heart rate, PR, QRS, QT, QTcF interval)

Statistical Analysis Plan Number CA36095

- Changes in vital signs from baseline (systolic and diastolic blood pressure, pulse rate, and respiratory rate)
- Concomitant medication
- Changes from baseline in clinical chemistry, hematology, and urine analysis safety panel
- 4. To describe the associations between PK and PD parameters.

Endpoints (Day 1 to Day 3):

- Between the score of "in the moment" product liking by the VAS-liking assessment averaged over the product use period (from T1 to T6) and during the sequence period (T1 to T9) and C_{max}, T_{max}, and AUC_{0-infinity} PK endpoints
- Between the average score of "in the moment" product satisfaction by the VAS product satisfaction assessment during the sequence's period (from T1 to T11) and Cmax, Tmax, and AUC0-infinity PK endpoints
- Between the score of "in the moment" craving by the VAS-craving assessment averaged during the sequence's period (from T1 to T11) and C_{max}, T_{max}, and AUC_{0-infinity} PK endpoints
- Between the subscale scores of PES and AUC_{0-infinity} PK endpoint
- Between the item scores of the Sensory questionnaire and AUC_{0-infinity} PK endpoint
- 5. To describe the extent of nicotine extracted during product use from 4 variants of NP 1.0, Velo-NP and Zyn-NP. This objective is not covered within the SAP and the reporting of this objective will be separate from the main CSR.

Endpoint (Day 1 to Day 3)

• Estimated amount of nicotine extracted derived from analysis of nicotine after use.

Study Hypothesis:

This study is exploratory in nature and there is no pre-specified hypothesis to be tested.

3. INVESTIGATION PLAN

[figure not shown]
3.1 STUDY DESIGN

This is a single-center, randomized, controlled, open-label, cross-over study in healthy smoking subjects to investigate the nicotine PK profiles of 4 variants of NP 1.0 compared to marketed Velo-NP and Zyn-NP. In addition, PD effects will be evaluated to provide further insights on NP 1.0 product acceptance and abuse liability. The study will be conducted with 6 product use periods and 6 sequences in a Williams design (cross-over).

A Screening Visit will be conducted within 21 days (Day -22 to Day -2) prior to Admission (Day -1) to the investigational site (Figure 1). Subjects will be screened against eligibility criteria.

Statistical Analysis Plan Number CA36095

Figure 1 Study Design

Qualified subjects will return to the investigational site for Day -1. Subjects should have fasted for at least 10 hours prior to the safety laboratory assessments. After confirmation of eligibility, subjects will be enrolled. All subjects that are not enrolled will be considered as screen failures.

On Day -1, enrolled subjects will perform a product test using NP-1 for 30 minutes (\pm 1 minute). After the product test, subjects not willing and/or not ready to use NP 1.0 during the study will be discontinued from the study, will enter the 3-day Safety follow-up period, and will be replaced.

Subjects willing and ready to use NP 1.0, Velo-NP and Zyn-NP during the study after product test will start their exposure period of 3 days.

Twenty-four (24) subjects will be randomized to 1 of 6 possible sequences of product use on Day 1 to Day 3 with at least 25% of each sex (see Figure 1). The randomization process including the randomization sequences will be documented in the randomization plan.

On Day 1 to Day 3, after at least 8 hours of abstinence from any nicotine/tobacco containing products (nicotine wash-out), subjects will use one NP for 30 minutes (± 1 minute) according to randomized product use sequence in the morning and in the afternoon, by placing the NP between the upper lip and gum. Subjects will complete self-reported assessments of product evaluation, craving, liking, satisfaction, and intent to use again.

The start of the 30 minutes use period will be defined as T₀. T₀ in the morning (T_{0M}) and in the afternoon (T_{0A}) on Day 1 to Day 3 should be approximately at the same time, within a window of \pm 30 minutes. Venous blood samples will be obtained according to the standard operating procedures (SOPs) at the investigational site.

Statistical Analysis Plan Number CA36095

On Day 1, 12 blood samples will be collected for determination of nicotine concentration at the following time points in relation to T_0 with a time window as indicated in brackets:

Morning prior to Tom and afternoon prior to Toa::

• T-1: 5 minutes (\pm 1 minute)

After Tom and Toa:

- T1 after 5 minutes (± 1 minute)
- T2 after 10 minutes (± 1 minute)
- T3 after 15 minutes (± 1 minute)
- T4 after 20 minutes (± 1 minute)
- T5 after 25 minutes (± 1 minute)
- T6 after 30 minutes (± 1 minute)
- T7 after 35 minutes (± 1 minute)
- T8 after 40 minutes (± 1 minute)
- T9 after 1 hour (± 5 minutes)
- T10 after 3 hours (± 5 minutes)
- T11 after 6 hours (± 5 minutes)

For each product use, subjective effects of liking, craving, satisfaction, and intention to use will be assessed at the following time points in relation to T0 with a time window as indicated in brackets:

Prior to Tom and Toa (for VAS craving only):

• T-15: within 15 minutes prior to T₀

After T_{OM} and T_{OA}: (for VAS craving, VAS liking "in the moment", and VAS satisfaction "in the moment" assessments):

- T1 after 5 minutes (± 1 minute)
- T2 after 10 minutes (± 1 minute)
- T3 after 15 minutes (± 1 minute)
- T4 after 20 minutes (± 1 minute)
- T5 after 25 minutes (± 1 minute)
- T6 after 30 minutes (± 1 minute)
- T7 after 35 minutes (± 1 minute)
- T8 after 40 minutes (± 1 minute)
- T9 after 1 hour (± 5 minutes)
- T10 after 3 hours (± 5 minutes) (VAS craving and VAS satisfaction only)
- T11 after 6 hours (± 5 minutes) (VAS craving and VAS satisfaction only)

After Tom and Toa: (for VAS liking (overall) assessment)

• T10 after 3 hours (± 5 minutes)

After Tom and Toa: (for VAS intention-to-use again)

• T6 after 30 minutes (± 1 minute)

Statistical Analysis Plan Number CA36095

• T10 after 3 hours (± 5 minutes)

Additional subjective effects will be assessed in the morning and in the afternoon on Day 1 to Day 3 by the PES and the Sensory questionnaire administered at T9, 1 hour (\pm 5 minutes) after T_{0M} and T_{0A}.

Additional blood samples will be taken for determination of the nicotine concentration to evaluate terminal elimination half-life (t1/2z) in relation to T0A on Day 2 at the following time points with a time window as indicated in brackets:

- T1z after 8 hours (± 5 minutes) after T_{0A}
- T2z after 12 hours (± 5 minutes) after T0A

After discharge at Day 3, the subjects will enter a 3-day Safety follow-up period during which AE/SAEs reported by the subjects associated with investigational product (IP) use will be collected and the follow-up of the ongoing AEs/SAEs will be conducted by the study investigational site.

Subjects who will be discontinued from the study before enrolment will be replaced. After enrollment but before randomization, subjects who will be discontinued from the study will enter the 3-day Safety follow-up period and will be replaced. However, subjects that are discontinued after randomization will not be replaced.

3.2 Selection of Study Population

Twenty-four healthy smoking subjects will be randomized to 1 of 6 possible sequences of product use on Day 1 to Day 3 with at least 25% of each sex.

The study population will be stratified by sex. Each sex will have a quota applied to ensure they represent at least 25% of the total randomized subjects.

3.2.1 Inclusion Criteria

Subjects who meet all the following inclusion criteria can be enrolled into the study:

	Inclusion Criteria	Screening	Admission (Day -1)
1.	Subject has signed the Informed Consent Form (ICF) and is able to understand the information provided in the ICF.	X	
2.	Smoking male or female aged between 21 and 65 years old.	X	
3.	Subject has smoked continuously for at least the last 3 years prior to the Screening visit.	X	
4.	Subjects has smoked ≥ 10 commercially available cigarettes per day for 4 weeks prior to Screening Visit and Admission. Smoking status will be verified based on a urinary cotinine test (cotinine ≥ 500 ng/mL).	X	X

Statistical Analysis Plan Number CA36095

	Inclusion Criteria	Screening	Admission (Day -1)
5.	Subject does not plan to quit using tobacco and/or nicotine products within the next 3 months.	X	X
6.	Smoking, healthy subject as judged by the Investigator or designee based on available assessments from the Screening period (e.g., safety laboratory, spirometry, vital signs, physical examination, ECG, and medical history).	X	

3.2.2 Exclusion Criteria

Subjects who meet any of the following exclusion criteria must not be enrolled into the study:

	Exclusion Criteria	Screening	Admission (Day -3)
1.	As per the Investigator's judgment, the subject cannot participate in the study for any reason other than medical (e.g., psychological, social reason).	X	
2.	Subject is legally incompetent, or physically or mentally incapable of giving consent (e.g., emergency situation, under guardianship, prisoners).	X	
3.	Subject has a clinically relevant disease which requires medication (including but not limited to gastrointestinal, renal, hepatic, neurological, hematological, endocrine, oncological, urological, immunological, pulmonary, and cardiovascular disease) or any other medical condition (including safety laboratory), which as per the judgment of the Investigator would jeopardize the safety of the subject.	X	
4.	As per the Investigator's judgment, the subject has medical conditions which require or will require in the course of the study, a medical intervention (e.g., start of treatment, surgery, hospitalization) which may interfere with the study participation and/or study results.	X	
5.	Subject has donated or received whole blood or blood products within 30 days prior to Screening Visit.	X	

Statistical Analysis Plan Number CA36095

	Exclusion Criteria	Screening	Admission (Day -3)
6.	Body Mass Index (BMI) $< 18.5 \text{ kg/m2 or} > 32.0 \text{ kg/m}^2$.	X	
7.	Subject has received medication within 14 days or within 5 half-lives of the drug prior to Admission (whichever is longer), which has an impact on CYP2A6 activity		X
8.	Subject has a positive serology test for HIV 1/2, Hepatitis B or Hepatitis C.	X	
9.	Subject has a history of alcohol abuse, which as per the judgment of the Investigator could interfere with the subject's participation in study.	X	
10.	Subject has a positive urine drug including alcohol test.	X	X
11.	Subject or one of their family members ^a is a current or former employee of the tobacco industry.	X	
12.	Subject or one of their family members ^a is employee of the investigational site or of any other contracted vendors involved in the study.	Х	
13.	Subject has participated in another clinical study within 30 days prior to the Screening Visit.	X	
14.	Subject has been previously screened or enrolled in this study.	X	
15.	For women only: subject is pregnant (does not have negative pregnancy test at Screening Visit and at Admission) or is breastfeeding.	Х	X
16.	For women of childbearing potential only ^b : subject does not agree to use an acceptable method of effective contraception ^c .	Х	Х
17.	Use of estrogen-containing hormonal contraception or hormone replacement therapy.	X	X

a. As defined by FDA guidance on Human Subject Protection (21 CFR 50.3(l), (m), 50.24(a)(6), (a)(7)(v), b)): "Family member" means among other things "parent", "spouse", "brothers, sisters, and spouses of brothers and sisters" and "any individual related by affinity...whose close association with the subject is equivalent of a family relationship"

- b. Women who are not of childbearing potential meet at least one of the following criteria:
 - Have undergone hysterectomy or bilateral tubal ligation,
 - Have primary ovarian insufficiency, or

Statistical Analysis Plan Number CA36095

- Are medically confirmed to be post-menopausal (cessation of regular menses for at least 12 consecutive months with no alternative pathological or physiological cause).
- c. Intrauterine device, intrauterine system, barrier methods of contraception (condoms, occlusive caps) with spermicidal foam/gel/film/suppository, hormonal contraception without estrogens, vasectomized partner(s), or true abstinence (periodic abstinence and withdrawal are not effective methods) from Screening until the end of the Safety follow-up period.

3.3 Discontinuation of Subjects from the Study

Discontinued subjects will include both, subjects who withdraw from the study (subject's decision) and subjects who are discontinued from the study by the decision of the Investigator. A subject can only be discontinued from the study after enrollment. Reason for discontinuation or withdrawal should be documented.

Subjects will be informed that they are free to withdraw from the study at any time. Subjects will be questioned for the reason for withdrawal from the study, although they are not obliged to disclose it.

The subject will be informed that if he/she withdraws from the study, the data collected until the point of withdrawal will be maintained as part of the study data and the samples collected prior to withdrawal will be analyzed, unless the subject disagrees in writing.

When a subject is discontinued or withdraw from the study, all early termination procedures (study protocol Section 9.7) will be performed unless the subject refuses to perform the assessments or the procedures have already been performed during the study day. This information will be fully documented by the Investigator.

Subjects must be discontinued from the study for any of the following reasons:

- Withdrawal of informed consent.
- Any AE/SAE or condition (including clinically significant changes in a laboratory parameter), which at the discretion of the Investigator is not compatible with the subject's continued participation in this study.
- Positive pregnancy test (study protocol Section 8.5).
- If the Sponsor decides to prematurely terminate the study, the subject will be promptly informed by the Investigator. The Investigator should report the fact and the reason in writing to the Independent Ethics Committee (IEC).
- Discontinuation is considered to be in the best interest of the subject, or the other subjects as judged by the Investigator, e.g. SARS-CoV-2 positive.
- Subject is not willing and/or ready to use NP 1.0 after the product test at Admission (Day -1).
- Subject uses any tobacco or nicotine containing product different from the assigned product during confinement.

Subjects may be discontinued from the study for the following reasons:

- Non-compliance to the study procedures based on the judgment of the Investigator.
- Violations of eligibility criteria have been determined (study protocol Section 5.4).

Subjects who will be discontinued from the study before enrolment will be replaced. After enrollment but before randomization, subjects who will be discontinued from the study will

enter the 3-day Safety follow-up period and will be replaced. In general, subjects that are discontinued after randomization will not be replaced.

4. ANALYSIS POPULATIONS

4.1 Analysis Populations

PK endpoints, PD endpoints, and amount of nicotine delivered will be analyzed using the PK population.

Safety will be analyzed using the safety population (SAF).

Demographics and baseline characteristics will be summarized in both SAF and PK populations.

4.1.1 Screened Population

The screened population consists of all subjects who underwent screening.

4.1.2 Safety Population (SAF)

The safety population (SAF) is a subset of the screened population and consists of all the subjects who signed ICF consent and have at least one exposure to NP 1.0 (including the product test with NP-1 at Admission).

4.1.3 Pharmacokinetic Population (PK)

The PK Population is a subset of the SAF and consists of all randomized subjects for whom at least one nicotine PK parameter can be derived. Only subjects without major protocol deviations, as defined in Section 4.2.1.1, which have an impact on evaluability of the main objective will be included in the PK population.

4.2 Protocol Deviations

Protocol deviations are defined as any departure from the procedures defined in the study protocol, including, but not limited to, any violation of inclusion/exclusion criteria, misrandomization, use of any nicotine or tobacco-containing product other than the assigned product during the exposure period, assessments not performed or performed outside the scheduled time windows, or use of medications that are known to affect study endpoints.

4.2.1 Data Collection

Protocol deviations will be entered into the clinical trial management system (CTMS) or other approved format. The data collected in the CRF may be used to assess protocol deviations from the data programmatically. Protocol deviations will be reconciled and categorized prior to locking the clinical database as described in the data management plan (DMP).

All deviations will be reviewed to determine their impact when subjects are assigned to analysis populations. Each deviation will be classified as major or minor.

Statistical Analysis Plan Number CA36095

4.2.1.1 Major Protocol Deviations

Subjects with major protocol deviations will be identified (at a population level) to determine whether they will be excluded from the PK population.

Major deviations will include but are not limited to the deviations presented in Table 4.1

Table 4.1 - Definition of Major Protocol Deviation Categories

Sub-Category	Description
Violation	Violation of inclusion/exclusion criteria
Mis-randomization	Violation of the product allocation process, including but not
	limited to the misclassification of subject's sex at randomization and incorrect product administered according to randomized sequence
Mis-use of product	Use of any nicotine or tobacco—containing product other than the assigned product during the exposure period or use of any nicotine tobacco-containing product during at least 10 hours of abstinence from any nicotine/tobacco containing products (nicotine wash-out).
	Product use not compliant with planned regimen of single product and 30 minutes product use period
Concomitant medications	Use of any drugs which are known to affect CYP2A6 activity

Among the eligibility criteria, violations of inclusion criteria 1, 2, 3, and 4 or of the exclusion criteria 2 and 14 will be considered as impacting the evaluability or integrity of the primary objective. Other major protocol deviations will be assessed for their impact on the evaluability of the primary objective during the pre-analysis data review meeting.

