At Day -1, enrolled subjects will perform a product test using NP-1 for 30 minutes (± 1 minute). After the product test, subjects not willing and/or not ready to use Nicotine pouch 1.0 during the study will be discontinued from the study, will enter the 3-day Safety follow-up period and will be replaced.

Subjects willing and ready to use Nicotine pouch 1.0, Velo-NP and Zyn-NP during the study after product test will start their exposure period of 3 days.

Twenty-four subjects will be randomized to 1 of 6 possible sequences of product use on Day 1 to Day 3 with at least 25% of each sex.

Confidentiality Statement

Philip Morris Products S.A.	Clinical Study Protocol	Confidential
P5-PK-01-EXP	2.0, Approved	Page 7 of 98

On Day 1 to Day 3, after at least 8 hours of abstinence from any nicotine/tobacco containing products (nicotine wash-out), subjects will use one nicotine pouch (NP) for 30 minutes (± 1 minute) according to randomized product use sequence in the morning and in the afternoon, by placing the NP between the upper lip and gum. Subjects will complete self-reported assessments of product evaluation, craving, liking, satisfaction, and intent to use again.

The start of the 30 minutes use period will be defined as T_0 . T_0 in the morning (T_{0M}) and in the afternoon (T_{0A}) on Day 1 to Day 3 should be approximately at the same time, within a window of \pm 30 minutes. Venous blood samples will be obtained according to the standard operating procedures (SOPs) at the investigational site.

On Day 1, 12 blood samples will be collected for determination of nicotine concentration at the following time points in relation to T0 with a time window as indicated in brackets:

Morning prior to T_{0M} and afternoon prior to T_{0A:}

• T-1: 5 minutes (± 1 minute)

After T_{0M} and T_{0A}

- T1 after 5 minutes (± 1 minute)
- T2 after 10 minutes (± 1 minute)
- T3 after 15 minutes (± 1 minute)
- T4 after 20 minutes (± 1 minute)
- T5 after 25 minutes (± 1 minute)
- T6 after 30 minutes (± 1 minute)
- T7 after 35 minutes (± 1 minute)
- T8 after 40 minutes (± 1 minute)
- T9 after 1 hour (\pm 5 minutes)
- T10 after 3 hours (\pm 5 minutes)
- T11 after 6 hours (± 5 minutes)

For each product use, subjective effects of liking, craving, satisfaction, and intention to use will be assessed at the following time points in relation to T0 with a time window as indicated in brackets:

Prior to T_{0M} and T_{0A} (for VAS craving only)

• T-15: within 15 minutes prior to T₀

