4.2 Rationale for Study Design

The minimum age of 21 years old in the inclusion criteria was selected based on the legal age of smoking in the United Kingdom of 18 years; and to account for the 3 years of smoking history.

The goal of this study is to evaluate the nicotine absorption profiles and related PK parameters from four variants of NP 1.0 compared to Velo-NP and Zyn-NP.

The 30 minutes use allow appropriate comparisons between different NP products [14]. The collection of PD data will also allow to explore effects of product liking on PK parameters.

Sampling time points for determination of nicotine concentrations were selected to ensure reliable estimation of PK parameters. In particular, frequent sampling between 20 to 50 minutes after T_0 will be performed in order to reliably assess T_{max} , which is expected to be comparable to what has been described previously e.g., for Zyn NP [14, 18].

The PK of plasma nicotine presents a biphasic profile, with a typical rapid initial disposition half-life $(t_{1/2\alpha})$ of 1.35 hours, followed by a slower terminal elimination half-life $(t_{1/2z})$ of 17 hours [19]. To ensure a complete nicotine washout between each product use, 3 days without product use would have been required (~ 5 x terminal elimination $t_{1/2z}$). Based on

Confidentiality Statement

Philip Morris Products S.A.	Clinical Study Protocol	Confidential
P5-PK-01-EXP	2.0, Approved	Page 36 of 98
D 1 . 1. 01 19 0015500		

nicotine population PK modeling, it was estimated that nicotine enters in the terminal elimination phase with concentrations decreasing with a terminal elimination rate constant (λ_z) 8 to 10 hours post administration. As a consequence, a minimum of 8 hours of nicotine abstinence has been established in this study prior to T₀ on Day 1 to Day 3. In order to estimate the λ_z three valid data points are needed to fit a regression line including estimation of error. The last data point is potentially not estimable (below LOD). Then four data points are likely required to estimate λ_z . Background-concentration correction will be applied to adjust for carry-over effects with adjustment of baseline values to the estimated t_{1/2z} (or λ_z) which will be derived from additional blood sampling on Day 2 and Day 3 for each subject.

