6.6 Restrictions

6.6.1 Smoking Restrictions

During the Screening period, subjects will be allowed to use any nicotine/tobaccocontaining products according to their usual habits except during the procedures of the Screening Visit (section 9.1). Spirometry assessment at Screening will be performed 1 hour after stopping smoking (section 9.1).

From Admission (Day -1) to Discharge (Day 3) or early termination, use of any nicotine/tobacco containing products, except use as per study design of the allocated product will not be permitted.

A nicotine washout period of at least 8 hours should be respected before T_{0M} and T_{0A} of NP use at Day 1 to Day 3.

Confidentiality Statement

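### SAP Table 4.1 grades nicotine abstinence on 10 hours where the protocol and SAP 3.1 require at least 8, and the SAP does not say how whole-subject PK exclusion relates to the estimand's period-level rule

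*SAP*

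**What the plan says.** **Abstinence interval.** SAP 4.2.1.1, Table 4.1, lists under mis-use of product the "use of any nicotine tobacco-containing product during at least 10 hours of abstinence from any nicotine/tobacco containing products (nicotine wash-out"). Everywhere else the nicotine interval is 8 hours:

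- Protocol Synopsis, Study Design: "after at least 8 hours of abstinence from any nicotine/tobacco containing products (nicotine wash-out), subjects will use one nicotine pouch (NP"). Protocol 4.1 and 6.2.2 repeat it.
- Protocol 4.2: "a minimum of 8 hours of nicotine abstinence has been established in this study prior to" the start of use on Days 1 to 3, with a pharmacokinetic reason given.
- Protocol 6.6.1: "A nicotine washout period of at least 8 hours should be respected before" both the morning and the afternoon start.
- SAP 3.1: "after at least 8 hours of abstinence from any nicotine/tobacco containing products (nicotine wash-out), subjects will use one NP".

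The only other 10-hour requirement in either document is fasting before safety laboratory tests. SAP section 9 lists two changes from the protocol, neither about abstinence, and declares the remaining analyses aligned.

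**What counts as a deviation.** SAP 4.2: "Protocol deviations are defined as any departure from the procedures defined in the study protocol". SAP 4.2.1 adds: "The data collected in the CRF may be used to assess protocol deviations from the data programmatically".

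**Handling.** SAP 4.1.3 and Protocol 12.2.3 keep a subject out of the PK population for a major deviation that affects evaluability of the main objective. SAP 4.2.1.1 names some eligibility violations as having that effect and leaves other major deviations to the pre-analysis data review meeting. Protocol 12.6.2, which SAP section 2 points to for the estimand, treats other-product use, use departing from 30 ± 1 minutes and broken abstinence as intercurrent events. For each, only the related period is set to missing, under missing at random (MAR).

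**The concern.** A grading table should grade departures from the procedure subjects were told to follow. Here it uses a different interval, so a subject with 8 to under 10 hours of abstinence complies with the protocol and has no deviation under SAP 4.2, yet meets the wording of a major one. The wording also covers any nicotine product, without the exemption that Protocol 6.6.1 makes: "except use as per study design of the allocated product". A program written from Table 4.1 could therefore flag the assigned morning pouch, used on schedule, as mis-use before the afternoon use.

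The label feeds the deviation summaries in SAP 4.2.2 and the review that settles the PK population. SAP 4.1 uses that population for all PK and PD endpoints.

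The second issue concerns what follows a genuine breach. The same events appear in Table 4.1 as possible grounds for whole-subject exclusion and in the estimand as reasons to blank one period. If a breach confined to one period removed the subject, valid periods would be lost and the analysis would depart from the stated estimand. Shortened use is the clearest case: Protocol 6.2 lets subjects stop at any time, and shortened use is not a mandatory reason for discontinuation, so up to five other periods are at stake. Use of a non-assigned product does require discontinuation (SAP 3.3), so there only the earlier periods matter.

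**Working it through.** **1. The two intervals.** Neither document gives the time between the morning and afternoon starts. Assume abstinence runs from pouch removal at 30 minutes.

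- 8-hour rule: afternoon start from 8 + 0.5 = 8.5 h after the morning start.
- Table 4.1 read literally: from 10 + 0.5 = 10.5 h.
- Upper end: the Day 2 sample at 12 h after the afternoon start should precede the Day 3 morning use. With start times held from day to day, the gap is at most about 24 − 12 = 12 h.
- Overnight: at least about 12 − 0.5 = 11.5 h of abstinence, which satisfies either figure.

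The texts therefore disagree for afternoon uses at 8.5 to under 10.5 h, within a feasible range of 8.5 to about 12 h. Where the real schedule falls is unknown.

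**2. The plan's precision figure.** Inputs (Protocol 12.9.5): n = 24, geometric CV of Cmax 40%, within-subject correlation 0.7, target 15% or less.

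- SD(log) = √ln(1 + 0.40²) = 0.3853
- SD of the within-subject log difference = 0.3853 × √(2 × (1 − 0.7)) = 0.2984
- Standard error = 0.2984 / √24 = 0.0609
- Precision = exp(t × standard error) − 1
- Paired, 23 df: t = 2.069, giving 13.4%
- Mixed model, 110 df: t = 1.982, giving 12.8%

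Both agree with the stated 15% or less.

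**3. Cost of each handling rule.** The mixed-model figures use generalized least squares on a six-product Williams square with four subjects per sequence. They assume compound symmetry with correlation 0.7, fixed sequence, period and product effects, and df = records − subjects − 10, averaged over random draws of the affected subjects and periods. The planned heterogeneous covariance would change them slightly.

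| Subjects affected | Whole subject out, mixed | Whole subject out, paired | One period out, mixed |
|---|---|---|---|
| 0 | 12.8% | 13.4% | 12.8% |
| 1 | 13.1% | 13.8% | 12.9% |
| 4 | 14.2% | 15.0% | 13.1% |
| 5 | 14.7% | 15.5% | 13.2% |
| 6 | 15.1% | 16.0% | 13.2% |

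With six affected, whole-subject exclusion leaves 144 − 36 = 108 records and period-level handling leaves 144 − 6 = 138. The 15% mark is passed at five exclusions (paired; four gives 14.99%) or six (mixed).

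**The case against.** The strongest reply is that the 10-hour wording has little force. Table 4.1 grades deviations, and SAP 4.2 defines a deviation as a departure from the protocol, so a compliant interval has nothing to grade. Even a wrong flag excludes nobody without an evaluability finding. Subjects are confined, pouches are dispensed singly, and use of another product is already covered by the first limb of the same row. What the 10-hour limb adds is mainly a flag on the assigned pouch, which the review would probably recognize as spurious. All of this stands as a limit on harm. It does not remove the contradiction, since SAP 4.2.1 permits programmatic detection and the deviation tables would carry the label.

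On handling, the natural reading is nested: the population says who is analysed, and the estimand says which of their data are blanked. The PK population needs only one derivable parameter, which admits subjects with partial data, and deciding evaluability before database lock is defensible in an exploratory study. This also stands. But SAP 6.5.1 never restates the period-level rule, and SAP 6.5.3 excludes by period only for a high pre-use concentration, so two teams could still treat the same subject differently.

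Three stronger inferences should be resisted. A reader might conclude that Table 4.1 drops compliant subjects automatically; SAP 4.1.3 and 4.2.1.1 do not say that. A reader might conclude that the PK-population rule contradicts the estimand; the nested reading is available. And a reader might take this review to decide which interval is right; it says only that the passages disagree.

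**Conclusion.** The interval mismatch is certain from the text: Table 4.1 uses 10 hours, while the procedure it grades is stated as 8 throughout the protocol and in SAP 3.1. The handling point is softer: it is an unstated relation between two compatible rules.

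The consequence is modest. The precision figures size only the whole-subject versus one-period choice, not the interval mismatch itself. They rest on the protocol's planning inputs and on a number of affected subjects that the documents do not give. One whole-subject exclusion costs about 0.3 percentage points. Passing 15%, which is a planning figure and not a success criterion, needs about five or six of 24 subjects removed. Any bias from departing from the estimand is not quantified. Severity is minor to should-fix, justified mainly because correction is cheap and should precede the data review.

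**What to change.** Amend the SAP before the data review meeting and before unblinding:

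- **Table 4.1.** Reconcile the 8-hour and 10-hour passages so that the table grades abstinence on the same interval as the protocol. State that scheduled use of the assigned pouch is not mis-use, in line with Protocol 6.6.1.
- **SAP 4.1.3 and 6.5.1.** State that a breach confined to one product-use period sets only that period to missing, as in Protocol 12.6.2, and that subject-level exclusion is kept for deviations affecting all periods.

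The cost is wording in three places, with no change to data collection. The second item needs no protocol amendment, because Protocol 12.2.3 leaves the definition of major deviations to the SAP and Protocol 12.1 allows method changes to be documented there. The first also stays within the SAP, unless the reconciliation were to alter the protocol's own interval.
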